##### B. Telangiectasia Scale

GRADE	EYELID MARGIN TELANGIECTASIA FINDINGS
0	No blood vessels present between meibomian glands.
1	One (1) blood vessel present between 4 pairs of glands/orifices
2	More than 1 vessel between 4 pairs of glands/orifices
3	More than 1 vessel with vasodilation between 4 pairs of glands/orifices.
4	More than 1 vessel with vasodilation between 4 pairs of glands/orifices with erythema of the tissue.

A certain score on the telangiectasia scale is not required for study entry, nor is it an exclusion criterion. The telangiectasia and meibomian orifice size scales will provide additional detailed information with which to track the progress/resolution of meibomian gland disease.

### 9.2.1.3. Tear Break-Up Time

A drop of Fluress® is added to the eye and the patient may blink once to disperse it. Then while the subject avoids blinking, the tear film is observed under the slit-lamp through a cobalt blue filter and timed until tiny dry spots develop. The procedure is conducted 3 times for each eye and the TBUT for each is measured in seconds and recorded in the eCRF. The average for each eye will be calculated by the eDC system.

### 9.2.1.4. Schirmer's Test (Anesthetized)

An anesthetized Schirmer's test will be performed to insure that only basal tear secretion is being measured and to prevent tearing due to the irritation from the filter paper (the eyes will already

have been anesthetized for the TBUT procedure). Filter paper strips will be placed in both eyes inside the lower eyelid (conjunctival sac) at the same time. The eyes are closed for 5 minutes. The paper is then removed and the amount of moisture on each strip in millimeters (mm) is measured and recorded in the eCRF.

### **9.2.2. Symptoms**

The OSDI questionnaire ([Appendix A](#)) will be provided to the study subject, who will be asked to circle the number that corresponds with the frequency of dry eye symptoms experienced over the past week. Site personnel will enter the scores in the eCRF. The eDC system will automatically calculate the final score.

## **9.3. Safety Assessments**

### **9.3.1. Slit-Lamp Examination**

A routine slit-lamp examination will be performed to evaluate the anterior segment of the eye, including lids, cornea, conjunctiva, anterior chamber, iris, and lens. Abnormalities will be documented.

## **9.4. Pharmacokinetic Assessment**

### **9.4.1. Omega-3 Index Test**

The Omega -3 Index Test measures the concentration of two specific omega-3 fatty acids, EPA and DHA, as a percent of total fatty acids in red blood cell membranes. This test is performed by using a contact-activated lancet to collect a drop or two of blood on a collection card. Each card is identified and packaged to be submitted to OmegaQuant (Sioux Falls, SD) for analysis.

## **9.5. Adverse and Serious Adverse Events**

### **9.5.1. Definition of Adverse Events**

#### **9.5.1.1. Adverse Event (AE)**

An AE is any untoward medical occurrence in a patient or clinical study subject administered a study medication (pharmaceutical/biological product) that does not necessarily have a causal relationship to this medication. An AE can therefore be any unfavorable and unintended sign (including abnormal laboratory findings), symptom, or disease temporally associated with the use of the study medication, whether or not related to the study medication. Study medication includes the investigational drug under evaluation and the comparator product or vehicle placebo that is given during any phase of the study.

Medical conditions/diseases present before starting the investigational treatment are only considered AEs if they worsen after starting the investigational treatment. Abnormal test results constitute AEs only if they induce clinical signs or symptoms, are considered clinically significant, or require therapy.

The occurrence of AEs should be sought by open-ended questioning of the subject at each visit during the study. At each clinic visit, study personnel should ask the following question: "Have

you had any problems since your last visit?" AEs also may be detected when they are volunteered by the subject during or between visits or through study assessments.

#### **9.5.1.2. Serious Adverse Event**

An SAE is any untoward medical occurrence that at any dose:

- Results in death,
- Is life-threatening,

Note: The term "life-threatening" refers to an event in which the subject was at risk of death at the time of the event; it does not refer to an event which hypothetically might have caused death if it were more severe.

- Results in persistent or significant disability/incapacity (excluding progression/outcome of the disease under study);
- Is a congenital anomaly/birth defect,
- Requires inpatient hospitalization or prolongation of existing hospitalization, or
- Is medically significant; ie, defined as an event that jeopardizes the health of the subject or may require medical or surgical intervention to prevent one of the outcomes listed above.

Treatment on an outpatient emergency basis that does not result in hospital admission, or a hospitalization that is elective or is a preplanned treatment for a pre-existing condition that is unrelated to the indication under study and has not worsened since the start of the study, is not considered an SAE.

All SAEs that are ongoing at the time of completion or discontinuation from the study will be followed until stabilization (i.e., no other change in the condition is expected) or resolution of the event.

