#### **8.5. Discontinuation of Study Medication**

Subjects may be discontinued from study medication for any of the following reasons:

- The subject has a clinically significant or serious AE that would not be consistent with continuation in the study, as determined by the Investigator or Medical Monitor
  - It is possible for subjects to experience a skin rash or other allergic reaction related to the components of the softgels; if this occurs, the subject should discontinue the medication.
- Pregnancy

If a subject is discontinued from study medication or is generally noncompliant with the protocol, every effort should be made to encourage the subject to continue to attend study visits

to be followed for safety, rather than withdrawing the subject from the study. Reasons for considering subject withdrawal from the study are discussed in Section 7.3.

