## **9.8. Reporting Adverse Events**

All SAEs (related and unrelated) will be recorded from signing of informed consent until the final study visit, Visit 3 (Day 42), following the end of treatment exposure. Any SAEs “suspected” to be related to the investigational product and discovered by the Investigator at any time after the study should be reported to Oculos.

Any SAE that occurs must be reported to Oculos within 24 hours of its occurrence or within 24 hours of learning of its occurrence. Recurrent episodes, complications, or progression of the initial SAE must be reported to Oculos as follow-up to the original episode within 24 hours of the Investigator receiving the information. Information about all SAEs will be collected and recorded on the SAE form. All pertinent medical records and information collected during the treatment and follow-up of the subject should be maintained at the site with a copy emailed to [[contact]](mailto:[contact]). The Investigator must assess the SAE relationship and complete the SAE form. Oculos may request additional information. Follow-up information (e.g., discharge summary) will be retained in the subject’s chart and a copy will be emailed to [[contact]](mailto:[contact]).

In addition, all SAEs should be recorded on the Adverse Event eCRF page with the serious question marked “Yes”.

It is the investigator’s responsibility to notify the approving IRB of any SAEs on a timely basis as instructed by the Sponsor or designee following the Sponsor’s determination of causality.

All subjects who experience an SAE should be followed clinically and undergo the appropriate diagnostic evaluations until stabilization or resolution of the event.

Oculos will report all SAEs to the US FDA on the appropriate schedule depending if the event is drug related or not drug related, expected, unexpected (based on the available information in the [Investigator’s Brochure](#)).

Any death occurring during the study and follow up period should be reported as an SAE. For any death occurring through the end of the study, regardless of the degree of relationship to study drug, the SAE resulting in the death must be reported to Oculos. A death occurring after completion of the study at Visit 4 (Day 84) does not require completion of the SAE form.

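### The exclusion of outpatient emergency treatment from the SAE definition is not limited to the hospitalization criterion and, read literally, conflicts with the life-threatening and medically significant criteria

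*Protocol*

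**What the plan says.** Protocol 9.5.1.2 lists six criteria joined by "or" in the sense that any one is enough. Three matter here:

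- Life-threatening, which "refers to an event in which the subject was at risk of death at the time of the event".
- Hospitalization: "Requires inpatient hospitalization or prolongation of existing hospitalization".
- Medically significant, meaning "an event that jeopardizes the health of the subject or may require medical or surgical intervention to prevent one of the outcomes listed above".

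A separate paragraph after the list carves out two things. The first is "Treatment on an outpatient emergency basis that does not result in hospital admission". The second is an elective or preplanned hospitalization for a pre-existing condition, subject to qualifiers. The sentence ends "has not worsened since the start of the study, is not considered an SAE". SAP 3.5.1.2 carries the same sentence. A paragraph on following up ongoing SAEs comes after it.

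Protocol 9.7 refers the question of seriousness back to the criteria in 9.5.1.2. Under Protocol 9.8 any SAE "must be reported to Oculos within 24 hours of its occurrence", or within 24 hours of the site learning of it. Protocol 8.5 foresees one relevant kind of event: "It is possible for subjects to experience a skin rash or other allergic reaction related to the components of the softgels".

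**The concern.** A definition of seriousness should give one answer for a given event. Here the list and the paragraph after it can give opposite answers for the same event: one that puts the subject at risk of death, or that needs intervention to avert a listed outcome, but is managed in an emergency department and discharged.

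The classification matters because several duties follow from SAE status. These are the 24-hour report, the SAE form, IRB notification and FDA reporting (Protocol 9.8), the explicit duty to follow the event until it resolves or stabilizes (Protocol 9.5.1.2, 9.7, 9.8), and the count of subjects with a treatment-emergent SAE (SAP 8.1). An allergic reaction of the kind foreseen in Protocol 8.5 is a natural example, provided that the reaction is in fact life-threatening or medically significant.

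**Working it through.** No arithmetic applies and the plan gives no figure to reproduce. The check is to set the texts side by side.

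**Step 1: which criteria depend on admission.** Only hospitalization does. Life-threatening turns on risk of death at the time of the event. Medically significant turns on jeopardy to health or on the possible need for intervention to prevent an outcome higher in the list. Inpatient hospitalization is one of those outcomes, so emergency treatment that averts an admission can itself bring an event within this criterion.

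**Step 2: what the exclusion is attached to.** Where 9.5.1.2 qualifies a single criterion, it does so at that criterion: the note on life-threatening sits under its own bullet, and the carve-out for disease progression is in parentheses inside the disability bullet. The outpatient exclusion stands alone after the whole list. Its conclusion concerns SAE status, not hospitalization, and it makes no exception for an event that meets another criterion.

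**Step 3: apply both readings.** The literal reading takes the exclusion as final. The narrow reading takes it as a gloss on the hospitalization criterion only.

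| Event | Criteria list alone | Literal reading | Narrow reading |
|---|---|---|---|
| Emergency treatment, sent home, no criterion met | Not an SAE | Not an SAE | Not an SAE |
| Life-threatening, emergency treatment, sent home | SAE | Not an SAE | SAE |
| Medically significant, emergency treatment, sent home | SAE | Not an SAE | SAE |
| Unplanned inpatient admission | SAE | SAE | SAE |

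The readings differ in the two middle rows, and there the literal reading contradicts the list.

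**Step 4: look for a tie-breaker.** Protocol 9.7 sends the reader back to 9.5.1.2. The SAP repeats the sentence without comment. Neither document states which text prevails.

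**Step 5: what follows if a site takes the literal reading.** The event is entered as an AE with the seriousness question answered no. Under Protocol 13.6 the eCRF entry is in general the source document, so that answer carries weight. The duties listed in Protocol 9.8 are not triggered, and the case is absent from the treatment-emergent SAE row in SAP 8.1, although it stays in the TEAE tables.

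**The case against.** The strongest reply is that the sentence is about care settings. Its grammatical subject is a treatment or a hospitalization, not the medical event, and both limbs concern admission. On that view it only clarifies the hospitalization criterion, and a life-threatening reaction treated without admission remains an SAE. This is a fair reading. It means that the text does not establish that the exclusion overrides the other criteria. What stands is that the text does not exclude the literal reading either.

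There are also backstops. Every AE is recorded, with a resolution date and time (Protocol 9.7). Monitors review entries remotely and flag safety signals to the Medical Monitor (13.5). Unmasking triggers a 24-hour contact that covers AEs as well as SAEs (8.2.1). A newly started systemic antihistamine or corticosteroid brings in the Medical Monitor (8.3.2). These are real, so the event would not vanish. But the first, second and fourth carry no 24-hour limit, and the third applies only if the subject is unmasked.

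A reader might infer three stronger points that the documents do not support:

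- *That any severe allergic reaction is affected.* Protocol 9.7 separates severity from seriousness, so only a reaction that also meets an SAE criterion is in question.
- *That the protocol names a serious hypersensitivity risk and then hides it.* Protocol 8.5 mentions rash or other allergic reaction and does not call it serious; exclusion criterion 1 also screens out known allergy to the components.
- *That reporting is delayed until the next scheduled visit.* The gap between visits governs when a site may first hear of an event, under either reading. The SAE clock also runs from the site's learning of the event, and AEs can be volunteered between visits (9.5.1.1). What is at risk is the 24-hour duty once the site knows.

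**Conclusion.** The point holds as an unresolved conflict within the SAE definition, present in both documents. Read literally, the exclusion removes SAE status from events that meet the life-threatening or medically significant criterion but are treated in an emergency setting without admission. It does not follow that such events will be misclassified, only that a site could do so while following the text.

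The size cannot be quantified: the documents give no rate of such events. The number may well be small. In the earlier trial of a similar product described in Protocol 4.2 (105 subjects), 4 subjects per group reported AEs, and all those in the active group were mild. The efficacy analyses are not affected. The conclusion assumes that no site training material, outside the two documents, already settles the reading. The correction is warranted because the passage governs expedited safety reporting and no backstop carries the general 24-hour duty.

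**What to change.** In Protocol 9.5.1.2 and SAP 3.5.1.2, keep both limbs of the sentence and every existing qualifier, but replace its conclusion with two statements:

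1. Such treatment or hospitalization does not by itself meet the hospitalization criterion.
2. The event is still an SAE if it meets any other criterion in the list, for example life-threatening or medically significant.

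The redraft must retain the condition that the pre-existing illness has no relation to the indication being studied. Dropping it would widen the hospitalization exclusion to dry-eye-related conditions.

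The cost is one reworded sentence in each document and a notice to sites, handled through the amendment route in Protocol 13.7. The downside is that a few more events may need an SAE form. No endpoint, procedure, dose or sample size changes.

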### **9.6. Relationship to Study Drug**

The relationship of AEs to the study medication should be assessed by the Investigator using the definitions below.

Not suspected: The temporal relationship of the event to the study medication makes a causal relationship unlikely, or, other drugs, therapeutic interventions or underlying conditions provide a sufficient explanation for the observed event.

Suspected: The temporal relationship of the event to the study medication makes a causal relationship possible or other drugs, therapeutic interventions or underlying conditions do not provide a sufficient explanation for the observed event.

If there is any valid reason, even if undetermined, for suspecting a possible cause-and-effect relationship between the study medication and the occurrence of the AE, then the AE should be considered "suspected."

If the relationship between the AE/SAE and the investigational product is determined by the Sponsor or designee to be “suspected” the event will be considered to be related to the investigational product for the purposes of expedited regulatory reporting (see Section 9.8).

## 9.7. Recording Adverse Events

Adverse events spontaneously reported by the subject and/or in response to an open question from the study personnel or revealed by observation, regardless of severity or potential association with the study medication or study procedures, will be recorded in the eCRF. Clinically significant changes in blood pressure and heart rate should be reported as AEs; however, Omega-3 treatment has been demonstrated to have beneficial effects on blood pressure and heart rate. Only clinically significant changes (increase or decrease) in heart rate should be reported as AEs. All AEs that occur after a subject has signed the informed consent form until the final study visit, Visit 4 (Day 84), should be collected and recorded on the AE eCRF page. AEs that occur after informed consent is provided but before the first dose of study medication will be summarized separately from AEs that occur from the first dose of double-masked treatment on Day 0 to the Day 84 visit. Serious adverse events will be followed until the event is resolved or stabilized.

Medical conditions/diseases occurring before the first dose of study medication during Visit 1 (Day 1) should be collected on the medical/ocular history pages of the eCRF.

The AE term should be reported in standard medical terminology when possible. For each AE, the Investigator will evaluate and report the following:

- Onset (date and time);
- Resolution (date and time);
- Severity grade (mild, moderate, severe);
- Relationship to study medication (not suspected, suspected);
- Action taken (none, study medication temporarily interrupted, study medication permanently discontinued; concomitant medication taken; hospitalization/prolonged hospitalization; other);
- Serious outcome (yes/no).

The severity grade should be determined by the Investigator using the definitions below.

- Mild: Discomfort noticed but no disruption of normal daily activity
- Moderate: Discomfort sufficient to cause interference with normal daily activity
- Severe: Incapacitating, with inability to perform normal activities

It is important to distinguish between serious and severe AEs. Severity is a measure of intensity (as defined directly above) whereas seriousness is defined by the criteria under Section 9.5.1.2. An AE of severe intensity may not be considered serious.

Should a pregnancy occur, it must be reported and recorded on the pregnancy form. Pregnancy in itself is not regarded as an AE unless there is a suspicion that an investigational product may have interfered with the effectiveness of a contraceptive medication.

The outcome of all pregnancies (spontaneous miscarriage, elective termination, normal birth or congenital abnormality) must be followed up and documented even if the subject was discontinued from the study.

## **9.8. Reporting Adverse Events**

All SAEs (related and unrelated) will be recorded from signing of informed consent until the final study visit, Visit 3 (Day 42), following the end of treatment exposure. Any SAEs “suspected” to be related to the investigational product and discovered by the Investigator at any time after the study should be reported to Oculos.

Any SAE that occurs must be reported to Oculos within 24 hours of its occurrence or within 24 hours of learning of its occurrence. Recurrent episodes, complications, or progression of the initial SAE must be reported to Oculos as follow-up to the original episode within 24 hours of the Investigator receiving the information. Information about all SAEs will be collected and recorded on the SAE form. All pertinent medical records and information collected during the treatment and follow-up of the subject should be maintained at the site with a copy emailed to [[contact]](mailto:[contact]). The Investigator must assess the SAE relationship and complete the SAE form. Oculos may request additional information. Follow-up information (e.g., discharge summary) will be retained in the subject’s chart and a copy will be emailed to [[contact]](mailto:[contact]).

In addition, all SAEs should be recorded on the Adverse Event eCRF page with the serious question marked “Yes”.

It is the investigator’s responsibility to notify the approving IRB of any SAEs on a timely basis as instructed by the Sponsor or designee following the Sponsor’s determination of causality.

All subjects who experience an SAE should be followed clinically and undergo the appropriate diagnostic evaluations until stabilization or resolution of the event.

Oculos will report all SAEs to the US FDA on the appropriate schedule depending if the event is drug related or not drug related, expected, unexpected (based on the available information in the [Investigator’s Brochure](#)).

Any death occurring during the study and follow up period should be reported as an SAE. For any death occurring through the end of the study, regardless of the degree of relationship to study drug, the SAE resulting in the death must be reported to Oculos. A death occurring after completion of the study at Visit 4 (Day 84) does not require completion of the SAE form.

## 10. STUDY ACTIVITIES

Note: Ophthalmic examinations should be conducted in the order listed in the Schedule of Procedures. All ophthalmic examinations are conducted in both eyes. Subjects must not have used any ophthalmic drop within 2 hours and must not have worn contact lenses within 12 hours of the study visit. Subjects determined to have used ophthalmic drops or worn contacts within the specified durations prior to study visits must be rescheduled.

### 10.1. Visit 1 (Day -7 to Day -1)/Screening

At Visit 1 (Day -7 to Day -1)/Screening subjects will provide written informed consent before any study-related procedures are conducted and participate in screening procedures to establish eligibility for the study. Procedures performed at Screening will include the following:

- Obtain written informed consent
- Inclusion/exclusion criteria
- Demographics
- Medical and ocular histories
- Concomitant medication history
- Urine pregnancy test (women of childbearing potential only)
- Tear osmolarity test
- Meibomian gland dysfunction grading
- TBUT
- Schirmer's test (anesthetized)
- Review inclusion/exclusion criteria
- AE assessment

Only subjects with tear osmolarity  $\geq 312$  mOsm/L and meibomian gland dysfunction grade **1 or 2** on the meibomian orifice size scale in at least one eye, and TBUT  $\leq 7$  seconds and Schirmer's test score  $\geq 5$  mm in both eyes will be scheduled to return to the clinical site for Visit 2. The qualifying osmolarity level and meibomian orifice size grade must be present in the same eye at Screening if only one eye qualifies.

